### **Participant Withdrawal**

Since participation is strictly voluntary, participants may withdraw at any time.

Participants will only be replaced if withdrawal occurs prior to the beginning of the first home assessment. Participants may be withdrawn due to non-compliance with study related procedures. Data from the baseline assessment or the subsequent data collection time points for participants who withdraw or who are lost to follow-up will be analyzed.

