Institution: University of Arkansas for Medical Sciences (UAMS) and Arkansas Children's Hospital/Research Institute (ACH/ACRI)

Sponsor: UAMS Translation Research Institute (UAMS TRI)

**Study Procedures, Outcome Measures, and Longitudinal Assessments:** For the proposed study, participants will receive home assessments for identification and reduction of asthma triggers via TM or standard of care asthma trigger education. Eligible subjects will undergo a total of 4 visits including an initial, in person screening/enrollment and initial demographic assessment visit, lasting approximately 1-2 hours. After enrollment and randomization, each TM participant will receive three home assessments including an initial baseline home assessment and two follow-up assessments, each 2 months apart (+/- two weeks). The home assessment visits will last approximately 90 minutes. During the TM home assessment, a home environmental asthma trigger assessment checklist (heat) will be utilized to identify potential asthma triggers in the subject's home. TM participants and their household will receive education and supplies, at the time of enrollment, for reduction of any identified triggers as well as education and supplies for general cleaning of the home. The Asthma Home Kit supplies provided to participants will include: Quickie 45TRI automatic sponge mop, child resistant roach and mice bait stations, zippered mattress covers, zippered pillow covers, trash can with lid, trash bags, anti-microbial sponges, rubber gloves, non-toxic all-purpose cleaner, Borax powder, scrubbing pads, Quickie home pro cleaning cloths, broom/dust pan, dusting spray, and paper towels. Each kit will contain labeled instructions on the proper use and/or storage of each item.

For those receiving standard of care education, each subject will receive the same education given to TM subjects for identification and reduction of asthma triggers, but will not receive TM home assessments or trigger reduction kits. Standard of care subjects will be contacted again at 2 months and 4 months (+/- 2 weeks) to assess retention of education materials and to provide additional asthma education and trigger reduction info. All participants will then receive a phone follow-up at 6 months (+/- two weeks) from the time of enrollment.

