Dust samples will be collected from all subjects in both study arms. We will use the Dustream collector (Indoor Biotechnologies) to collect the dust specimens. Subjects will receive a dust collector kit that attaches to a vacuum cleaner. All participants will receive written instructions at the time of enrollment but will also be contacted by TM to assist with proper collection of the dust samples. These samples will be mailed to the study team using pre-paid postage and packaging through the USPS. One sample will be collected from the main living area and another sample will be collected from the participant's sleeping area during the baseline visit. A second set of dust samples will be collected at the 4 month visit for both groups.

Each participant will be contacted by phone at 6 months for an end of study visit. This phone conversation should last approximately 15-30 minutes. In the event the participant is no longer available on the day of the scheduled follow-up visits or 6-month phone contact, three attempts will be made to complete study procedures/ end of study phone call. If the research staff are unsuccessful after the third scheduled visit or phone call attempt, an email will be sent to the parent/caregiver asking that he/she contact the research staff via return phone call.

Protocol v8 5/27/2021

Title: Efficacy of Telemedicine Home Assessments for Identification and Reduction of

Asthma Triggers

PI: [name]

Institution: University of Arkansas for Medical Sciences (UAMS) and Arkansas Children's Hospital/Research Institute (ACH/ACRI)

Sponsor: UAMS Translation Research Institute (UAMS TRI)

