### **Data Analysis**

#### **Sample size:**

*Analysis for the primary endpoint:* The primary outcome measure is level of dust mite allergens as measured by the MARIA™ test data. Using a one-way analysis of covariance, we estimated that a sample size of 20 in each of the two groups will yield at least 96% power to detect a 4  $\mu\text{g/g}$  difference between group means assuming a common standard deviation of 2 and a two-sided significance level of 5%.

Title: Efficacy of Telemedicine Home Assessments for Identification and Reduction of

Asthma Triggers

PI: [name]

Institution: University of Arkansas for Medical Sciences (UAMS) and Arkansas Children's Hospital/Research Institute (ACH/ACRI)

Sponsor: UAMS Translation Research Institute (UAMS TRI)

**Analysis for the secondary endpoint:** To evaluate the secondary outcome variables, the distribution for each outcome (i.e. home environmental asthma trigger score (heat), ACT score, healthcare utilization, visit satisfaction, and education recall) will be first assessed with summary statistics and graphical measures. It is anticipated that the distribution for some of these variables will be positively skewed. In cases of non-normal data, a logarithmic or square root transformation will be applied to normalize the distribution of the data. Secondary outcomes will be assessed for significant differences between groups and from baseline to 4 months and 6 months using a univariate repeated measure analysis of variance that will include a time x group interaction.

All tests will be two-sided and assume a significance level of 5%. All statistical analyses will be performed using SAS software version 9.4 (SAS Institute Inc., Cary NC, USA).

**Missing data and general considerations:** All reasons for drop out and missing data will be documented and reported. Subjects will be replaced if the dropout rate exceeds the estimate of 10%.

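### Withdrawal for non-compliance may leave the 4-month dust result missing in a way tied to adherence, probably in favour of the telemedicine arm

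*Combined protocol and SAP*

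**What the plan says.** The Participant Withdrawal section gives staff discretion: "Participants may be withdrawn due to non-compliance with study related procedures". It sets no threshold, names no decision-maker and does not distinguish the arms. It then says: "Data from the baseline assessment or the subsequent data collection time points for participants who withdraw or who are lost to follow-up will be analyzed".

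Under Study Procedures, Outcome Measures, and Longitudinal Assessments, TM families have three video home assessments two months apart, and "The home assessment visits will last approximately 90 minutes". Standard-of-care families have education contacts at 2 and 4 months. Other procedures are shared: "Dust samples will be collected from all subjects in both study arms", and both arms complete questionnaires and a 6-month call. For the primary outcome, "A second set of dust samples will be collected at the 4 month visit for both groups"; Table 1 shows no other post-baseline dust measurement. A participant who is unavailable for a scheduled visit gets three attempts and then an email.

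The Data Analysis section says: "All reasons for drop out and missing data will be documented and reported". It defines no analysis set and no method for missing outcomes. Replacement of participants is mentioned in both sections, on different conditions.

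**The concern.** Non-compliance is observed after randomisation and may be related to both the arm and the dust level. Once a family is withdrawn before month 4, the promise to analyse its data covers only what was collected. A baseline value alone cannot enter a comparison of change to 4 months. The attempts-and-email rule is for missed appointments and does not say that staff still pursue a sample from someone they have withdrawn. Replacement would restore the head count but not the missing result.

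Specific Aim 1 asks how effective the TM programme is against standard education. Whether families engage is part of that answer. If less engaged families drop out of the primary comparison, the estimate moves towards the effect in families who complied. Each family is 5% of a 20-family arm, so one or two withdrawals can matter.

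**Working it through.** **Inputs from the documents.** 20 per arm, difference 4 µg/g, SD 2, two-sided 5%, power of at least 96% (Data Analysis, Sample size); dust at baseline and 4 months only (Table 1).

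**Assumptions, not in the documents.** D = 4 µg/g is the benefit in adherent TM families and non-adherent ones get none; q is the non-adherent share; w is the share of those withdrawn before month 4; a family without a 4-month sample is not in the primary comparison.

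**1. The plan's own figure.** Standard error = 2 × √(2/20) = 0.632 µg/g, and 4/0.632 = 6.32. Power is about Φ(6.32 − 1.96) = Φ(4.36), above 99.99%. The noncentral t with one covariate gives 99.999%, and 99.99% with 18 per arm. This satisfies the stated minimum but does not reproduce 96%. On these inputs lost power is not the issue; bias is.

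**2. Overstatement.** The as-randomised effect is D(1 − q). After withdrawal the retained share of TM is (1 − q) + q(1 − w) = 1 − qw, so the observed effect is D(1 − q)/(1 − qw). The ratio of the two is 1/(1 − qw).

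| q | w | As randomised | Observed | Overstatement |
|---|---|---|---|---|
| 0.1 | 0.5 | 3.60 | 3.60/0.95 = 3.79 | 5% |
| 0.1 | 1 | 3.60 | 3.60/0.90 = 4.00 | 11% |
| 0.2 | 0.5 | 3.20 | 3.20/0.90 = 3.56 | 11% |
| 0.2 | 1 | 3.20 | 3.20/0.80 = 4.00 | 25% |

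**3. Equal withdrawal in both arms.** Let non-adherent families have dust levels g higher whatever their arm. With the same q and w in each arm, both means shift by gq(1 − w)/(1 − qw), and the shift cancels. The table is unchanged, so imbalance between arms is not needed when only adherent families benefit.

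**4. Families who would have sent no dust anyway.** Let s be the share of withdrawn families who would otherwise have supplied a sample. Without the rule the observed effect would be D(1 − q)/(1 − qw(1 − s)). With q = 0.2, w = 1 and s = 0.5 that is 3.20/0.90 = 3.56, so the rule accounts only for the step from 3.56 to 4.00, or 12.5%. With s = 0 it accounts for nothing.

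**5. No treatment effect.** Simulation with 20 per arm, SD 2, q = 0.2, g = 2 µg/g and 8,000 runs (negative favours TM):

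| Non-adherent families withdrawn | Mean difference | Type I error |
|---|---|---|
| All, TM only | −0.40 | 8.4% |
| Half, both arms | 0.00 | 4.7% |
| All, standard of care only | +0.41 | 8.5% |

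The shift is qg = 0.2 × 2 = 0.4. With D = 4 the same 0.4 applies: TM-only withdrawal would give 4.0 + 0.4 = 4.4, and standard-of-care-only withdrawal 3.2 − 0.4 = 2.8, against 3.2 as randomised. Imbalance can therefore add to the overstatement or reverse it.

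**The case against.** The strongest reply is that the direction is not in the documents. The rule is permissive and covers both arms, many procedures are shared, and no withdrawal rates by arm are given. Standard-of-care families receive no supplies and might disengage as readily. This stands as a limit on certainty. It does not remove the concern, because step 3 shows inflation under equal withdrawal when benefit depends on adherence. Balance gives zero bias only when there is no treatment effect.

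Second, families who miss visits may not post dust either, and the last TM assessment falls at 4 months, so only failures at the first two assessments or soon after can lead to withdrawal before the primary measurement. This also stands, and it reduces the size (step 4).

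Third, the sentence on analysing withdrawn participants' data refers to later time points and can be read as allowing further collection. It does not exclude it, but it commits nobody to seek the sample.

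Fourth, the 10% case is a bias of 0.4 µg/g, below the standard error of 0.63, and even 3.2 is about five standard errors from zero (3.2/0.632 = 5.1). On the plan's inputs the significance test is hardly at risk. The point concerns the estimate and its meaning.

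A reader might also infer that failing to use the supply kit is grounds for withdrawal. No section measures kit use or makes it a compliance requirement, so the argument rests on visit burden alone. A reader might call the trial open. The documents do not mention blinding; that staff know the allocation is a fair inference, since the home visitor delivers both arms, but it is not stated. Coded dust samples mask the laboratory and cannot recover a missing sample.

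**Conclusion.** The concern holds as a risk. A discretionary rule, with no commitment to collect the 4-month sample afterwards, may cause adherence-related missing data in the primary comparison, probably favouring TM. The overstatement is about 5% to 25% for 10–20% non-adherence with half to all of those families withdrawn. That range assumes benefit confined to adherent families, and either balanced withdrawal or no difference in dust level between adherent and non-adherent families. It also assumes that withdrawn families would otherwise have supplied a sample.

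A reader might infer that the rule does remove mainly TM families, so that the trial compares compliant TM families with all standard-of-care families. The documents do not support that. It is one extreme pattern, and the opposite imbalance would understate the effect. For a 40-child pilot this is a change that should be made because it is cheap; it does not invalidate the design.

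**What to change.** In Participant Withdrawal, state that non-compliance with sessions is not a reason to end data collection and that only withdrawal of consent ends it. In the study procedures, ask every randomised participant for the 4-month dust sample and the 4- and 6-month questionnaires, whether or not sessions were completed. In Data Analysis, state that the primary analysis is by allocated arm. Record session attendance and report adherence descriptively by arm.

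If everyone is followed to 4 months and analysed as randomised, the bias from this rule is zero. The cost is a few sentences in these sections and a few more contact attempts; the pre-paid mailing of samples already exists. The estimate will be somewhat diluted, for example 3.2 instead of 4.0 µg/g in the 20% case, but that is the effect of offering the programme.

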### **Risks and Benefits**

A potential risk to study participants is the potential for loss of confidentiality. Measures to protect confidentiality will be implemented according to UAMS/ACH/ACRI policies.

There are no significant risks to participants regarding the home assessment products being used. All products utilized in cleaning of the home or with the reduction in asthma triggers are non-toxic. The pesticides in the bait traps should not be handled by young children or pregnant individuals during their first trimester. We recommend the participant/household family member read all labeled warnings prior to opening the package. There are no significant risks associated with use of telemedicine as the connection is via secure link with ACH.

There could be no direct benefits to the study participants. Potential benefits to participation include improved education of participating subjects and family members in regards to identification and removal of asthma triggers. Participants in the TM group will be provided supplies to assist with reduction in home asthma triggers throughout the study period. This may improve the participant's asthma morbidity leading to decreased healthcare utilization. Knowledge gained from the study could also potentially benefit patients in the future.

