### **Secondary Outcome Measures:**

**Asthma Control Test (ACT):** The ACT is a validated 5-question ( $\geq 12$  years of age) or 7-question ( $<12$  years of age) survey used to assess asthma control. ACT is used for symptoms monitoring as per guidelines and has been identified as an appropriate asthma control composite score in clinical research.

**Healthcare Utilization:** At baseline, participants will be surveyed to determine the number of acute exacerbations he/she has experienced in the past 12 months resulting in hospitalization, emergency room/sick visits, or systemic steroid use. At each study time point, participants will record acute exacerbations resulting in hospitalization, emergency room or sick visits, or systemic steroid use since the previous asthma education session/TM home assessment visit.

**Visit Satisfaction:** We will administer ACH's outpatient satisfaction survey, supplied by National Research Corporation, at the completion of each visit for both groups. For TM

Title: Efficacy of Telemedicine Home Assessments for Identification and Reduction of

Asthma Triggers

PI: [name]

Institution: University of Arkansas for Medical Sciences (UAMS) and Arkansas Children's Hospital/Research Institute (ACH/ACRI)

Sponsor: UAMS Translation Research Institute (UAMS TRI)

participants, we will administer the telemedicine patient satisfaction survey that will ask respondents to assess four areas regarding the effectiveness and quality of care received via TM: 1) risk and benefits, 2) effectiveness, 3) efficiency, and 4) future adoption.

**Education Recall:** Participants and household parents/caregivers will be administered a questionnaire at each follow-up visit and again via phone call at 6 months to assess recall of education provided during each home assessment.

The ACT, healthcare utilization, visit satisfaction and education recall questionnaires will be completed via a mobile link and take approximately a total of 20 minutes to complete.

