### **Data Handling and Recordkeeping**

The Principal Investigator will carefully monitor study procedures to protect the safety of research subjects, the quality of the data and the integrity of the study. All study participant material will be assigned a unique identifying number. Only study staff will have access to the code and information that identifies the participants in this study. Questionnaires, consent and assent forms will be stored in a binder in a locked protected file in a locked office on ACH campus. Only study personnel will have access to these forms. All participant materials will be recorded in a REDCap database utilizing the unique subject identifier to protect the confidentiality of the individuals. Maintaining a link to identifiers until after data analysis is complete allows for rechecking of data to ensure data integrity and improved study design. For dust samples, only the unique identifying number will be used to identify subject samples during shipping to the processing lab. Samples will be discarded after lab analysis. At the end of the study, documents will be archived according to UAMS/ACH/ACRI policies regarding destruction of research records. Electronic records will be stored on the ACRI/UAMS servers which are password protected.

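### The plan has no systematic collection of non-asthma harm from the home kit, although it names a pesticide precaution

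*Combined protocol and SAP*

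**What the plan says.** Under Study Procedures, Outcome Measures, and Longitudinal Assessments, the TM arm alone receives the home kit. It includes "child resistant roach and mice bait stations", along with Borax powder, an all-purpose cleaner and a dusting spray, and it is supplied at enrollment.

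Risks and Benefits makes three statements about these products. The first is a general assurance: "There are no significant risks to participants regarding the home assessment products being used". The second describes every kit product, whether for cleaning or for trigger control, as non-toxic. The third is a handling precaution that follows directly on that description: "The pesticides in the bait traps should not be handled by young children or pregnant individuals during their first trimester".

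On oversight, Data Handling and Recordkeeping says: "The Principal Investigator will carefully monitor study procedures to protect the safety of research subjects". The sentence goes on to data quality and study integrity. It defines no event, question, schedule or reporting route.

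On events, the Healthcare Utilization paragraph of Secondary Outcome Measures says: "At each study time point, participants will record acute exacerbations resulting in hospitalization, emergency room or sick visits, or systemic steroid use". Table 1 has five rows: dust mite levels, ACT, healthcare utilization, satisfaction and information recall. Data Analysis describes no safety summary.

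**The concern.** The plan identifies a hazard in something it places in the homes of children as young as 5, in one arm only. It then asks families, at each contact, about asthma and about nothing else that could go wrong. A swallowed product, an eye splash or a skin reaction is not an asthma exacerbation, so it falls outside the definition of what is recorded.

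This matters because the gap cannot be closed at analysis: events that were not asked about during follow-up cannot be reliably recovered afterwards. A pilot whose intervention includes a kit of household products will be asked whether the kit was acceptable to place in homes. As planned, it would have asthma outcomes, satisfaction and recall to offer, and no systematically collected product-harm data.

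**Working it through.** The plan contains no safety figure to reproduce. The check is therefore textual first, followed by a calculation of what collecting the data could show.

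**Step 1. Routes by which a kit-related harm in the participant could reach the data**

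| Where in the document | What it covers | Would it capture a non-asthma harm? |
|---|---|---|
| Table 1 | Five outcome measures, listed above | No row for it |
| Healthcare Utilization | Exacerbations leading to hospital, emergency or sick visits, or systemic steroids | Outside the definition |
| ACT | Asthma control at baseline, 2, 4 and 6 months, both arms | No; respiratory effects only |
| Screening, initial demographic assessment and informed consent | Health record access, for asthma utilization | Outside the stated purpose |
| Telemedicine satisfaction survey | A risk-and-benefit area about care delivered by TM, TM arm only | Not about the kit; items not reproduced |
| Missing data and general considerations | Reasons for dropout | Only if the harm led to dropout |
| Data Handling and Recordkeeping | Investigator oversight of study procedures | No event or question defined |
| Data Analysis | Power for the primary outcome; analysis of secondary outcomes | No safety summary |

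Two partial routes exist (respiratory effects through ACT and exacerbations, and dropout reasons). Neither reaches an ingestion, contact or reaction in a child who stays in the trial.

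**Step 2. What zero reported events would show**

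Inputs: 20 TM participants (40 randomized 1:1; Sample size). The plan's 10% dropout estimate, applied here to the TM arm as an assumption, leaves 20 × 0.90 = 18.

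The exact upper limit with no events in n is 1 − 0.05^(1/n) for a one-sided 95% limit and 1 − 0.025^(1/n) for a two-sided 95% interval.

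| n | One-sided 95% | Two-sided 95% |
|---|---|---|
| 20 | 1 − 0.05^(1/20) = 13.9% | 1 − 0.025^(1/20) = 16.8% |
| 18 | 1 − 0.05^(1/18) = 15.3% | 1 − 0.025^(1/18) = 18.5% |

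**Step 3. The chance that asking would reveal anything**

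The documents give no event rate, so a range is assumed. The chance of at least one participant with an event is 1 − (1 − p)^n.

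| Assumed true rate p | n = 20 | n = 18 |
|---|---|---|
| 1% | 18.2% | 16.5% |
| 2% | 33.2% | 30.5% |
| 5% | 64.2% | 60.3% |
| 10% | 87.8% | 85.0% |

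The item would probably show a harm that is fairly common and would probably miss a rare one.

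**The case against.** The case on the other side has several parts.

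- **Respiratory harm is partly covered.** Airway irritation from a cleaner, powder or spray is the effect most relevant to these children. It could show in ACT and exacerbations, compared between randomized kit and no-kit arms. That comparison needs no event-by-event attribution. This stands, though 20 per arm gives it little power. A reader might infer that no harm from the kit could be detected at all; the documents do not support that.
- **The plan mitigates the hazard.** The bait stations are child resistant, the kit carries labelled instructions, and the home visitor goes through use and storage of every item by video at the first TM visit. These steps reduce risk but do not collect data.
- **The visible text may be incomplete.** Table 1 is a summary and omits the home trigger score that is used elsewhere. The visit descriptions mention other surveys that are not reproduced, and consent pages were removed. The point is therefore limited to what the document plans. Injury-contact wording in a consent form would not in any case be planned data collection.
- **The oversight sentence is narrow.** A reader might infer a broken promise to monitor safety events. The text commits the investigator to monitoring study procedures in order to protect safety, which is less than that.
- **Silence is not a claim of zero.** A reader might infer that the trial would report no product harm whatever happened. The plan has no harm count, so it would report nothing on the subject.
- **Reports would be hard to interpret.** The participants know their arm and only the TM arm is coached on the products, so self-attributed reactions may be reported differently by arm. This stands, and it is why the counts should be descriptive.

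**Conclusion.** The gap is real and limited. Non-asthma harm from the kit in the participant is not systematically collected anywhere in the visible plan, and the plan's own pesticide precaution is reason enough to ask. Nothing here suggests that the kit is unsafe, and no primary or secondary result is affected.

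A reader might also infer that collecting these events would test the statement that the products carry no significant risk. It would not: even a clean result among all 20 TM participants is compatible with a true rate of up to 13.9% or 16.8%, depending on sidedness. The gain is that the pilot could give a bounded statement where it now can give none. This conclusion rests on the reading of the text in Step 1; the limits assume complete answers from the stated number of participants.

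Separately, describing all the products as non-toxic sits badly beside the precaution on handling the bait-trap pesticides in the same paragraph. The two statements need to be reconciled.

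**What to change.** 1. Add one item to the 2-, 4- and 6-month questionnaires in both arms: since the last contact (since enrollment, at 2 months), has the participant had any accidental ingestion, contact or reaction linked to a cleaning or pest-control product? If so, record the date and whether care was sought. Ask the control arm too, since those homes may use such products of their own. Restrict the item to the enrolled participant, because other household members have not consented to having health events recorded.
2. Add a matching row to Table 1.
3. State that the principal investigator reviews each positive answer.
4. In Data Analysis, state that the number of participants with any such event is reported by arm, descriptively, with exact limits and the number who answered.
5. Reconcile the non-toxic description with the pesticide precaution in Risks and Benefits.

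The cost is one question at contacts already scheduled, one table row, one descriptive table and a minor amendment through the IRB. The downsides are some non-specific reports and possible differential reporting by arm. Sample size, treatment and the primary analysis do not change.
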